6.2. Other Endpoints

6.2.1. PK Endpoints

There are no PK endpoints in this study.

6.2.2. PD Endpoints

There are no PD endpoints in this study.

6.2.3. Outcomes Research Endpoints

There are no Outcomes Research endpoints in this study.

6.3. Covariates

There are no statistical models that will be fitted for the data in this study, and so there are no definitions of covariates.

Data will be summarized by parent study.

7. HANDLING OF MISSING VALUES

Data will be reported based on observed findings. No data will be imputed except as described next. Where a Week 24 summary is shown, it will relate to observed data collected at the Week 24/Early Termination visit and within the Week 24 window defined in [Appendix 1.1](#). Additionally, data for the last observation carried forward (LOCF) will be presented for Week 24. This data can be thought of as a type of LOCF assessment, where the investigator has brought forward subject assessment from the point of early termination to the Week 24/Early Termination visit.

8. STATISTICAL METHODOLOGY AND STATISTICAL ANALYSES

8.1. Statistical Methods

8.1.1. Analyses for Continuous Data

Continuous endpoints will be summarized using the following statistics: number of subjects, arithmetic mean, standard deviation, median, minimum, and maximum values. These statistics will be shown by treatment group and overall.

8.1.2. Analyses for Categorical Data

Categorical data will be summarized by parent study and treatment group.

8.1.3. Analyses for Binary Endpoints

The incidence of subjects with total joint replacement and specific adjudication outcomes (listed below) will be summarized for all combined osteoarthritis studies. This incidence are shown by treatment group (with a tanezumab combined group, and a total for that parent study). The events to be analyzed are:

- Total Joint Replacement.
- Total Joint Replacement, with outcome adjudicated as:
 - Any of Rapidly Progressive Osteoarthritis (RPOA) type 1 or 2, Subchondral insufficiency fracture (SIF), Primary Osteonecrosis (ON), Pathological Fracture;
 - Any of RPOA type 2, SIF, Primary Osteonecrosis, Pathological Fracture;
 - RPOA type 1 or 2;
 - RPOA type 1;
 - RPOA type 2;
 - ON;
 - Pathological Fracture;
 - SIF;
 - Not enough information to determine rapid or Normal Progression of OA;
 - Normal Progression of OA;
 - Other Joint Outcome.

The analysis will show the number of subjects with the event, the number of subjects in the parent study treatment group (using the ‘Safety Analysis Set’),

An overall summary of subjects with events (total joint replacement and then by adjudication outcome) for all combined osteoarthritis studies and by study will be shown, overall and by treatment group. In addition, two types of summarization, subject level with primary outcome and joint level, will be prepared for adjudicated outcome.

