5.3. Safety Analysis Set

The ‘Safety Analysis Set’ (SAS) is the analysis set for all analyses. It consists of all treated subjects who enrolled in Study A4091064, and who have a qualifying total joint replacement for Study A4091064. This analysis set is used in the presentations of all data summaries and listings and is labeled as the ‘Safety Analysis Set’ or ‘SAS’.

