5.4. Other Analysis Sets

No other analysis sets are defined.

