At the Week 4, 12 and 24 post-surgery telephone contacts, subjects will be queried for rehabilitation activities related to the replaced joint. Specifically, subjects will be asked to respond yes or no to the following question:

- *Are you participating in physical rehabilitation activities related to your replaced joint?*

Subjects will be queried for details if the answer to the question is yes.

The data relating to the endpoints of physical rehabilitation, or additional or corrective procedure, related to the replaced joint up to Week 24 will be derived from an ongoing clinical review of the concomitant non-drug treatment/procedure case report form (CRF) page. This review will identify treatments that are relevant for these endpoints, and a log of such data will be maintained. The data relating to the endpoint of concomitant analgesic medication use will be derived from an ongoing review of the concomitant analgesic drug CRF page. These reviews will be made during the study and data will be finalized prior to the database release for this study.

Events identified as the first symptom leading to total joint replacement will be reviewed and determined prior to the unblinding for the respective parent study.

The list of post-surgical complications will be derived from reported adverse events and will consist of complications that are clinically significant and attributable to the total arthroplasty procedure eg, periprosthetic joint infection/wound infection, periprosthetic fracture, pulmonary embolism or sepsis/septicemia/shock. The list of post-surgical complications will be developed during Study A4091064 and finalized prior to Study A4091058 unblinding. Other adverse events may be identified as post-surgical complications after the unblinding of the Study A4091058 database. These events will also be summarized as complications, and will be noted as having been included in the list after the unblinding of the Study A4091058 database.

Adverse Events which are “treatment emergent” in relation to the Baseline study day will be reported overall and by prior study treatment group. Adverse events ongoing from the parent study will continue to be followed in this study. They will not be included in incidence tables from this study unless the severity worsens.

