8.2. Statistical Analyses

8.2.1. Analysis of Endpoints

All subjects enrolled in the study who have a qualified total joint replacement will be included in the summary tables. In addition, three types of endpoints, the surgeon’s assessment of procedural difficulty, the subject’s overall satisfaction, and concomitant

nondrug treatment, will be summarized for subjects who were adjudicated with RPOA (type 1 and 2), RPOA (type 1), RPOA (type 2), Primary ON, SIF, or NPOA.

The events considered in the incidence of event summary are total joint replacement and total joint replacement with specific individual or grouped adjudication outcomes, as defined in [Section 8.1.3](#).

Unless otherwise stated, data from this study will be presented at Baseline and Weeks 4, 12, and 24 using observed data (no imputation for missing data), and at Week 24 using Last Observation Carried Forward (LOCF) for missing data. Data will be shown at the timepoints specified and also using change from (pre-surgery) Baseline when Baseline data are available and where relevant. Data will be shown overall, and split by treatment group. Data on surgical difficulty and outcomes, and subject safety data will be summarized by study (if needed), with an additional combined summary for the subjects from the osteoarthritis studies.

For the Surgeon's Assessment of Procedural Difficulty, the number and percentage of subjects in each category (Uneventful, Minor complications, Major complications) will be presented. Complications reported by the surgeon will be listed.

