8.2.2. Summary of Analyses

Endpoint	Time points	Analysis Set	Statistical Method	Model/ Covariates/ Strata	Missing Data	Objective
Summary of total joint replacement (TJR) and adjudication outcomes (Joint Level)	Any time during parent study or 1064	SAS	None	N/A	Observed	Summary of frequency and the proportion
Summary of detail of adjudication outcomes (Joint Level)	Any time during parent study or 1064	SAS	None	N/A	Observed	Summary of frequency and the proportion
Summary of total joint replacement (TJR) and adjudication outcomes (Subject Level)	Any time during parent study or 1064	SAS	None	N/A	Observed	Summary of frequency and the proportion
Summary of detail of adjudication outcomes (Subject Level)	Any time during parent study or 1064	SAS	None	N/A	Observed	Summary of frequency and the proportion
Surgeon's assessment of procedural difficulty by TJR joint and total (All OA parent studies)	Assessed after surgery	SAS	None	N/A	Observed	Summary of surgical outcome
Subject's overall satisfaction with surgery by TJR joint and Total (All OA parent studies)	Week 4, 12, 24	SAS	None	N/A	Observed	% and frequency of each category
Subject's overall satisfaction with surgery by TJR joint and Total (All OA parent studies)	Week 4, 12, 24 and 24 (LOCF)	SAS	None	N/A	Observed (LOCF for Week 24 (LOCF))	Summary of surgical outcome
Physical rehabilitation in relation to replaced joint by TJR joint and Total (All OA parent studies)	Any time post-surgery	SAS	None	N/A	Observed	Summary of surgical outcome
Additional or corrective procedures relating to TJR by TJR joint and Total (All OA parent studies)	Any time post-surgery	SAS	None	N/A	Observed	

Endpoint	Time points	Analysis Set	Statistical Method	Model/ Covariates/ Strata	Missing Data	Objective
Average Pain in the joint to be replaced/replaced joint by visit and change from BL by TJR joint and Total (All OA parent studies)	BL, Week 4, 12, 24, 24 (LOCF)	SAS	None	N/A	Observed (LOCF for Week 24 (LOCF))	Summary of surgical outcome
WOMAC Pain, Physical Function and Stiffness subscales by visit and change from BL by TJR joint [Hip/Knee] and Total (All OA parent studies)	BL, Week 4, 12, 24, 24 (LOCF)	SAS	None	N/A	Observed (LOCF for Week 24 (LOCF))	Summary of surgical outcome
SPADI dimensions and total by visit and change from BL (All OA parent studies)	BL, Week 4, 12, 24, 24 (LOCF)	SAS	None	N/A	Observed (LOCF for Week 24 (LOCF))	Summary of surgical outcome

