Post-surgical complications (All OA parent studies)	Any time post-surgery	SAS	None	N/A	Observed	
Concomitant analgesic medication use (All OA parent studies)	Any time post-surgery	SAS	None	N/A	Observed	Summary of surgical outcome
Subpopulation summary of Surgeon's Assessment of Procedural Difficulty for subjects who had RPOA (type 1 and type2), RPOA (type 1), RPOA (type 2), primary ON, SIF, or NPOA	BL, Week 4, 12, 24, 24 (LOCF)	SAS	None	N/A	Observed	Subgroup presentation
Subpopulation summary of Subject's Overall Satisfaction for subjects who had RPOA (type 1 and type2), RPOA (type 1), RPOA (type 2), primary ON, SIF, or NPOA	BL, Week 4, 12, 24, 24 (LOCF)	SAS	None	N/A	Observed	Subgroup presentation

Endpoint	Time points	Analysis Set	Statistical Method	Model/ Covariates/ Strata	Missing Data	Objective
Subpopulation summary of concomitant nondrug treatment for subjects who had RPOA (type 1 and type2), RPOA (type 1), RPOA (type 2), primary ON, SIF, or NPOA	Any time post-surgery	SAS	None	N/A	Observed	Subgroup presentation

SAS: Safety analysis set for subjects with TJR and entered into 1064

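### The SAP's by-arm TJR incidence is computed only among enrolled TJR subjects (100% by construction), and the exposure-adjusted rates, risk contrasts and Kaplan-Meier summaries in Protocol 9.2 are absent from the SAP

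*SAP*

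**What the plan says.** SAP 8.1.3 plans the incidence of TJR, and of TJR by adjudicated outcome, for the combined osteoarthritis studies: "This incidence are shown by treatment group (with a tanezumab combined group, and a total for that parent study". It gives the denominator as "the number of subjects in the parent study treatment group (using the ‘Safety Analysis Set". SAP 8.2.1 uses the same term: "The events considered in the incidence of event summary are total joint replacement", alone and with adjudicated outcomes.

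SAP 5.3 defines the Safety Analysis Set (SAS), used for every analysis: "It consists of all treated subjects who enrolled in Study A4091064, and who have a qualifying total joint replacement for Study A4091064". SAP 5.4 adds: "No other analysis sets are defined". The footnote to the SAP 8.2.2 table agrees: "SAS: Safety analysis set for subjects with TJR and entered into 1064". Four rows of that table cover TJR and adjudication, for example "Summary of total joint replacement (TJR) and adjudication outcomes (Subject Level". All four use the SAS, list no statistical method, and aim at frequency and proportion.

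For A4091058, Protocol 9.2 plans TJR percentages and exposure-adjusted rates by arm. It also plans tanezumab versus active comparator risk differences and ratios with 95% confidence intervals, and Kaplan-Meier summaries of time to TJR and time to first symptom from the first subcutaneous dose. The time-to-event summaries are planned for A4091056 and A4091057 as well. SAP 6.1 keeps the preparatory step for one of these: "Events identified as the first symptom leading to total joint replacement will be reviewed and determined prior to the unblinding" of the parent study.

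**The concern.** An incidence needs a denominator of people who could have had the event or not. Here, having had the event is a condition of entry to the denominator. A table headed by treatment arm then carries no information on whether TJR was more frequent in one arm than another. The adjudication rows do vary, and the method text calls them incidence, so they could be read as the risk of rapidly progressive osteoarthritis, subchondral insufficiency fracture or osteonecrosis by arm. Protocol 1.2.3.2.2 names rapidly progressive osteoarthritis as the identified risk, so that misreading matters.

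The by-arm TJR analyses still promised in Protocol 9.2 also cannot be produced from the only population that the SAP defines. A reader with both documents cannot tell which analyses the report will contain.

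**Working it through.** There is no plan figure to reproduce: the estimate of fewer than 250 enrollees (Protocol 9.1) comes without inputs.

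**1. Subject-level TJR row.** Every SAS member has a qualifying TJR, so for an arm with n members the proportion is n/n = 1. Taking 20, 30 and 60 enrollees in three arms: 20/20 = 30/30 = 60/60 = 100%. Any risk difference is 0 and any risk ratio is 1, whatever the counts.

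**2. Adjudication rows.** The risk of a given diagnosis in an arm is

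P(TJR | treated) × P(diagnosis | TJR).

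The SAS rows estimate only the second factor, and only among enrollees. If one arm had twice the TJRs of another with the same diagnosis mix, these rows would agree although every diagnosis-specific risk was doubled.

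**3. The two documents side by side.**

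| Protocol 9.2 | SAP |
|---|---|
| A4091058 TJR percentages by arm | A by-study, by-arm proportion is kept, but on the SAS (100%) |
| Exposure-adjusted rates by arm | Absent |
| Risk differences and ratios, 95% CI | Absent; every 8.2.2 row lists the method as None |
| Kaplan-Meier, time to TJR | Absent |
| Kaplan-Meier, time to first symptom | Absent, although 6.1 still derives the events |
| Time-to-event summaries, A4091056 and A4091057 | Absent |

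**4. What a parent-study denominator could show.** Protocol 1.2.3.1 plans N = 1000 per A4091058 arm (randomized, used here as a proxy for treated). The documents give no TJR counts, so those below are assumptions. Intervals: Newcombe for the risk difference; for the risk ratio, exp(ln RR ± 1.96 × SE) with SE = √(1/x₁ − 1/n₁ + 1/x₀ − 1/n₀).

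- 20 versus 20: SE = √(0.049 + 0.049) = 0.313. Risk difference 0 (−1.3 to 1.3 points); risk ratio 1.0 (0.54 to 1.85).
- 40 versus 20: SE = √(0.024 + 0.049) = 0.270. Risk difference 2.0 points (0.5 to 3.6); risk ratio 2.0 (1.18 to 3.40).

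The SAS row reads 100% versus 100% in both cases.

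**5. Why the numerator matters too.** Protocol 1.2.4 accepts that some subjects with a qualifying TJR will not enter A4091064. Assume 60 versus 30 TJRs per 1000 (risk ratio 2.00), with 60% and 90% enrolling. Counting enrollees only gives 60 × 0.6 = 36 versus 30 × 0.9 = 27, a risk ratio of 1.33. Changing the denominator alone is therefore not enough.

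**The case against.** The strongest reply is that the SAP is allowed to differ. Protocol 9 lets it modify the planned analyses and asks for an amendment only when a change is major. No objective and none of the nine co-equal endpoints concerns TJR risk, and the SAP's amendment history shows that the analysis set and Section 8 were revised deliberately. A reader might infer a breach of the amendment rule. The documents do not establish that, because they do not say what counts as major. What stands is that the two current texts disagree; the amendment history does not name the removal of these analyses.

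Protocol 9.2 itself opens by putting enrolled TJR subjects in the summary tables, so the ambiguity starts there. Yet its exposure-adjusted rates and its Kaplan-Meier origin at first dose make sense only for a wider treated population.

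The denominator sentence in SAP 8.1.3 breaks off at a comma and may be a remnant of a parent-study denominator. That is possible, but SAP 5.3, SAP 5.4 and the 8.2.2 footnote lead to the same result without it.

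The 8.2.2 titles speak of summaries and proportions, so the labelling fault is confined to the method text in 8.1.3 and 8.2.1. This limits the risk of misreading but does not supply the missing analyses.

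Two other replies fail. SAP 3 has TJR incidence summarized program-wide for the data monitoring committee, but that does not replace the reported analysis. SAP 4 excludes inferential testing, but Protocol 9.1 also calls all analyses descriptive and Protocol 9.2 plans these estimates nonetheless.

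**Conclusion.** The point holds and should be fixed. The 100% result follows from the definitions alone and needs no assumption, but it covers only the subject-level TJR row. The adjudication rows vary, and the joint-level denominator is not stated. The absence of the exposure-adjusted rates, contrasts, intervals and Kaplan-Meier summaries is read directly from the SAP text and its analysis table. The intervals in the working rest on assumed counts: they show what a parent-study analysis might yield and do not measure the defect.

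Three stronger inferences are not supported:

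- That the post-operative results are compromised. The SAS suits those endpoints, and the secondary comparison in A4091058 concerns outcome after surgery, not the risk of surgery.
- That expected enrolment caps TJR risk at 250/4500 = 5.6% per arm (4500 = 690 + 810 + 3000). That is a pooled ceiling on enrollees. If all came from A4091058 it would be 250/3000 = 8.3%, and subjects who decline are not counted.
- That the plan would produce Kaplan-Meier curves falling to zero. Neither document plans a Kaplan-Meier analysis on the SAS.

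**What to change.** In SAP 5, add a parent-study treated population: all subjects given subcutaneous treatment in A4091056, A4091057 or A4091058. Use it as the denominator for subject-level TJR and adjudicated-outcome incidence, and restore the Protocol 9.2 analyses on it, including the time-to-event summaries for A4091056 and A4091057. Count every adjudicated TJR recorded in the parent studies, enrolled or not, and show by arm how many of those subjects did and did not enrol. State that surgeries after parent-study exit in subjects who decline A4091064 may be missed, since Protocol 4.1 also admits surgery that was only planned during the parent study. Keep the SAS for post-operative outcomes. The cost is SAP text, some programming, and use of parent-study counts, exposure time and adjudications.

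If the sponsor means to report TJR risk only in the parent-study reports, then instead relabel the SAP text and tables as the distribution of adjudicated outcomes among enrolled TJR subjects, drop the unused first-symptom derivation in SAP 6.1, and amend Protocol 9.2. This is cheaper, but it only reconciles the wording and adds nothing on risk by arm.

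Either way, complete the broken sentence in SAP 8.1.3 and state the joint-level denominator.

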8.2. Statistical Analyses

8.2.1. Analysis of Endpoints

All subjects enrolled in the study who have a qualified total joint replacement will be included in the summary tables. In addition, three types of endpoints, the surgeon’s assessment of procedural difficulty, the subject’s overall satisfaction, and concomitant

nondrug treatment, will be summarized for subjects who were adjudicated with RPOA (type 1 and 2), RPOA (type 1), RPOA (type 2), Primary ON, SIF, or NPOA.

The events considered in the incidence of event summary are total joint replacement and total joint replacement with specific individual or grouped adjudication outcomes, as defined in [Section 8.1.3](#).

Unless otherwise stated, data from this study will be presented at Baseline and Weeks 4, 12, and 24 using observed data (no imputation for missing data), and at Week 24 using Last Observation Carried Forward (LOCF) for missing data. Data will be shown at the timepoints specified and also using change from (pre-surgery) Baseline when Baseline data are available and where relevant. Data will be shown overall, and split by treatment group. Data on surgical difficulty and outcomes, and subject safety data will be summarized by study (if needed), with an additional combined summary for the subjects from the osteoarthritis studies.

For the Surgeon's Assessment of Procedural Difficulty, the number and percentage of subjects in each category (Uneventful, Minor complications, Major complications) will be presented. Complications reported by the surgeon will be listed.

For the subject's overall satisfaction with surgery assessments (using the Self-Administered Patient Satisfaction scale, SAPS), the responses [score] for each category (Very Satisfied [100], Somewhat Satisfied [75], Somewhat Dissatisfied [50], Very Dissatisfied [25]) will be stratified by surgery type (hip, knee or shoulder) and summarized for each of the four items. The scale score is the unweighted mean of the scores from the individual items, ranging from 25 to 100 per item with higher scores indicating greater satisfaction. This total score (mean of the 4 items) will be summarized by surgery type (hip, knee or shoulder) and overall. Responses to the question "How satisfied are you with the results of your surgery?" will also be stratified by surgery type (hip, knee or shoulder) and summarized as satisfied (very satisfied and somewhat satisfied categories combined) and dissatisfied (somewhat dissatisfied and very dissatisfied categories combined).

The total satisfaction score will be summarized using the mean (with standard deviation), median, and minimum and maximum values. These results will be shown by visit, with Week 24 (LOCF).

Similarly, the number and percentage of subjects who have required (i) additional or corrective procedures related to their total joint replacement and (ii) participating in physical rehabilitation activities related to their replaced joint will be presented. For this assessment, change from Baseline summary data are not relevant and will not be presented. This summary will be shown separately for total joint replacements of the hip, knee and shoulder, as well as shown overall. These summaries will be shown for any post-surgery timepoint. Average pain (NRS) in the replaced joint for all subjects, WOMAC Pain, Stiffness and Physical Function sub-scale scores for subjects who had total knee or hip replacement and SPADI Pain, Function and Total Score for subjects who had total shoulder replacement will be summarized (including change from Baseline summaries).

In addition, the number and percent of subjects with specified post-surgical complications will be presented. The list of post-surgical complications will be derived from reported adverse events and non-drug treatment/procedure. It will consist of complications that are clinically significant and attributable to the total arthroplasty procedure eg, periprosthetic joint infection/wound infection, periprosthetic fracture, pulmonary embolism or sepsis/septicemia/shock. The list of post-surgical complications will be developed during Study A4091064 and finalized prior to Study A4091058 unblinding. Other adverse events may be identified as post-surgical complications after the unblinding of the Study A4091058 database. These events will also be summarized as complications, and will be noted as having been included in the list after the unblinding of the Study A4091058 database.

Adverse events and concomitant analgesic medications will be collected for each subject during the study according to the Schedule of Assessments. Standard safety reporting tables will summarize and list these safety data.

Separate adverse event summaries by parent study treatment group for adverse events of abnormal peripheral sensation, and sympathetic nervous system will be presented. Adverse event summaries of decreased sympathetic function may be presented.

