3. INTERIM ANALYSES, FINAL ANALYSES AND UNBLINDING

The final analysis for this study will be performed after the database has been released.

The incidence of subjects with total joint replacements, and resulting adjudicated outcomes will be summarized throughout the tanezumab program. This includes the parent studies of this protocol (A4091056, A4091057, and A4091058), this study itself, and other tanezumab studies (A4091059, A4091061, and A4091063). These analyses will be produced for the Data Monitoring Committee (DMC) and will be unblinded to the DMC members. These analyses will be produced by a separate unblinded group at Syneos who are separate from the corresponding study team at both Syneos and Pfizer.

Information from this study will be blinded for the parent study treatment group until the parent study itself has been unblinded.

In all cases the adjudication of joint safety events is made in a blinded fashion by the adjudication committee.

Interim analyses of these data may be produced for inclusion in a regulatory submission. In this case, a snap-shot of the database will be taken and stored. If this interim analysis occurs, then all parent study databases would have been finalized and those studies unblinded, therefore it is not envisioned that subjects would be unblinded due to this interim analysis.

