Appendix 2. UNBLINDING PLAN

1. Introduction

The A4091064 is the long-term observational study without dosing to follow up subjects who undergo total joint replacement (TJR) of knee, hip or shoulder from one of parent studies (A4091056, A4091057, or A4091058) or sub-studies (A4091059, A4091061, or A4091063), and one of the secondary objectives is to compare the post-operative outcomes for tanezumab 2.5mg and 5 mg versus NSAIDs for subjects who underwent a TJR in A4091058.

The purpose of this unblinding plan is to describe who can access to the unblinding information of parent phase 3 studies (and sub-studies) while A4091064 is ongoing and the rationale. The goal is to maintain the double blind (subjects and investigator) at any study sites and among operational colleagues interacting with site directly about patient data in order to minimize the potential to introduce bias for comparison of the post-operative outcomes.

2. Rationale for Unblinding of Parent Phase 3 Studies to A4091064 Study Team Members

The rationale for the appropriateness of this approach for unblinding includes the following:

- Major endpoints to evaluate TJR follow-up of A4091064 are based on patient and/or surgeon reported outcomes, and an investigator or Pfizer study team will not evaluate them.
- All endpoints of A4091064 will be summarized descriptively and there is no formal hypothesis testing.
- A4091064 is a study being incorporated into the data package for regulatory submission. Pfizer team needs to evaluate TJR based on the data of both A4091064 and these parent studies (and sub-studies) simultaneously with considering these relationships by representatives who are familiar with these studies.
- No changes will be made to A4091064 study designs, conduct, or analysis based on the parent phase 3 studies unless the program is terminated or otherwise modified for safety findings, in which case, the changes would be reflected in a protocol amendment.

3. Unblinding Prior to Database Release of any Parent Phase 3 Studies

The phase 3 program is using a safety monitoring committee (SMC), which will have access to unblinded data throughout the parent phase 3 studies for the monitoring of subject safety. A separate SMC charter specifies the role and responsibilities of the SMC and the contact individuals within the Pfizer's organization and the SMC responsible for communication between these organizations.

4. At or after Database Release of any Parent Phase 3 Studies

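### Complications identified after A4091058 unblinding are counted in the same co-equal endpoint, with no closed-list count planned and no blinding rule specific to that step

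*SAP*

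**What the plan says.** SAP section 6.1 makes post-surgical complications up to Week 24 one of the co-equal endpoints, counted in subjects. An event qualifies if it is clinically significant and can be attributed to the arthroplasty.

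- **Closing the list.** SAP 6.1 and 8.2.1 carry the same rule: "The list of post-surgical complications will be developed during Study A4091064 and finalized prior to Study A4091058 unblinding". Protocol section 9.2 also closes the list, before A4091058 database lock, and has no step for reopening it.
- **Reopening it.** Both SAP sections continue: "Other adverse events may be identified as post-surgical complications after the unblinding of the Study A4091058 database". On how such events are handled: "These events will also be summarized as complications, and will be noted as having been included in the list after the unblinding".
- **Planned output.** SAP 8.2.1 promises one number and percent of subjects. The table in SAP 8.2.2 has a single row, which begins "Post-surgical complications (All OA parent studies". On display by parent study, SAP 8.2.1 says "subject safety data will be summarized by study (if needed), with an additional combined summary for the subjects from the osteoarthritis studies".
- **Blinding.** SAP section 3 says "Information from this study will be blinded for the parent study treatment group until the parent study itself has been unblinded". SAP Appendix 2, section 4.1, then unblinds at subject level all A4091064 team members not listed in section 4.2. Section 4.2 keeps blind the investigator sites, the sponsor clinician who deals with sites on joint replacement evaluation, the regional site lead and certain contract-organisation roles.

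**The concern.** A secondary objective compares tanezumab 2.5 mg and 5 mg with NSAID among A4091058 subjects, and complications are one of the outcomes compared. The list is fixed while treatment is masked, but the endpoint can grow once treatment is known. If the person deciding which further events qualify can see the arms, terms that are commoner in one arm could be favoured or passed over, even unintentionally. The reported percentages would then partly reflect that choice.

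Two things would protect the reader: a percentage on the list as it stood before unblinding, and an assurance that later decisions were made blind. The SAP provides for neither. The flag on late events helps, but it marks events or terms, while the endpoint counts subjects.

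**Working it through.** The documents give no figure for this endpoint (no alpha, power or expected rate), so there is nothing to reproduce. The check has three parts.

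**1. Does any blinding rule cover the late classification?**

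| Provision | What it secures | Does it cover this step? |
|---|---|---|
| SAP 3 | Masking until the parent study is unblinded | No: for A4091058 subjects the late window opens when this masking ends |
| Protocol 5 | Directly involved sponsor staff blinded, no end date given | Not reliably: the SAP says its unblinding plan was added in relation to this section, and that plan unblinds part of the team |
| Appendix 2, section 4.1 | Unblinds everyone not listed in 4.2 | Works the other way |
| Appendix 2, section 4.2 | Sites and listed roles stay blind | Only if a listed role does the classifying, and none is assigned |
| Appendix 2, section 2, fourth bullet | "No changes will be made to A4091064 study designs, conduct, or analysis based on the parent phase 3 studies", apart from safety-driven changes | Unclear: it does not say whether adding a complication is a change of analysis |
| Appendix 2, section 2, first bullet | Major endpoints "are based on patient and/or surgeon reported outcomes, and an investigator or Pfizer study team will not evaluate them" | Does not describe an endpoint that has to be classified by review |

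No provision names the person who makes late additions or requires that person to be blind.

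**2. Can the closed-list percentage be read from the planned summary?** Not necessarily. Take a hypothetical arm of 83 in which 7 subjects have any complication and a flagged late term occurs in 3 of them. If none of the 3 has a listed event, the closed-list count is 7 − 3 = 4, or 4/83 = 4.8%. If all 3 also have a listed event, it is 7, or 7/83 = 8.4%. The same table fits both.

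**3. How much does one added subject matter?** Shift in an arm's percentage = 100/n. The documents do not give n, so it is assumed here.

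Inputs from protocol sections 1.2.3.1 and 9.1:
- Randomised per arm: A4091056 690/3 = 230; A4091057 810/3 = 270; A4091058 3000/3 = 1000.
- Planned duration: 40, 48 and 80 weeks.
- Enrolment in A4091064: estimated below 250, so 250 is a ceiling.

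Pooled osteoarthritis arms by randomised numbers (total 4500):
- 2.5 mg: 230 + 270 + 1000 = 1500; 250 × 1500/4500 = 83.3; shift 1.20 points.
- 5 mg: 270 + 1000 = 1270; 250 × 1270/4500 = 70.6; shift 1.42 points.
- NSAID: 1000; 250 × 1000/4500 = 55.6; shift 1.80 points.

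Pooled arms by planned subject-weeks (3 × (230×40 + 270×48 + 1000×80) = 306,480):
- 2.5 mg: 102,160; n = 83.3; shift 1.20 points.
- 5 mg: 92,960; n = 75.8; shift 1.32 points.
- NSAID: 80,000; n = 65.3; shift 1.53 points.

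A4091058 alone: 55.6 or 65.3 per arm on the same two splits, or 250/3 = 83.3 if every subject came from that study. The shifts are 1.80, 1.53 and 1.20 points.

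If the same addition brings one subject into every pooled arm, the NSAID minus 2.5 mg difference moves by only 1.80 − 1.20 = 0.60 points (randomised split) or 1.53 − 1.20 = 0.33 points (subject-weeks). If only the NSAID arm gains a subject, it moves by 1.80 or 1.53 points. At an assumed 125 enrolled, every shift doubles.

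**The case against.** The strongest defence is that late additions are proper in a safety study. Complications can arise up to 24 weeks after surgery, possibly after A4091058 is unblinded, and a rigid list could leave real events uncounted. The SAP fixes a list in advance and discloses departures from it. The events themselves are reported by sites that stay blind. The wording speaks of inclusion in the list, which suggests adding terms for all subjects rather than picking cases by arm. SAP 8.2.2 is an index of analyses rather than a set of table shells, so one row does not prove that only one column will appear, and a closed-list count could be derived from subject-level data. All of this stands, and it keeps the severity low. It does not close the gap: an unblinded person choosing terms could still favour those concentrated in one arm, and a count that could be derived is not a planned count.

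Some stronger readings are tempting but unsupported:

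- *Late events will be classified by unblinded staff.* The documents allow this but do not say it. A role that stays blind under section 4.2 could do the work.
- *There is no blinding protection at all.* Protocol 5 and Appendix 2 contain general safeguards. What is missing is one tied to this step.
- *The SAP breaches the protocol.* Protocol section 9 lets the SAP modify the planned analyses, so the difference from protocol 9.2 is not in itself a breach.
- *The SAP applies a stricter rule to a comparable endpoint.* First-symptom events are settled before parent unblinding, but a first symptom precedes the surgery, whereas complications follow it. The timing explains the different cut-off.
- *Type I error is inflated.* SAP 4.2 rules out inferential testing.

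**Conclusion.** The point holds as a gap in the plan. A judged, co-equal endpoint can be extended after A4091058 unblinding, no closed-list result is planned, and no blinding requirement is attached to the extension. The consequence is a possible bias in a descriptive comparison of tanezumab with NSAID. That such bias will occur is not established.

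Its size cannot be derived: the documents give neither the number of late additions nor the unblinding date, and protocol 9.1 calls the distribution across treatment groups unknown. The figure of about 1.2 to 1.8 points per added subject shows leverage only. It rests on the 250-subject ceiling and on joint replacements arising in proportion to randomised numbers or planned follow-up, or all coming from A4091058. Smaller enrolment would raise it, while adding an event type in all arms would largely offset it in the difference. Confidence is high about the wording gap, not about any bias. This is a cheap improvement of low severity.

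**What to change.** 1. **SAP 6.1, 8.2.1 and 8.2.2:** by treatment group, report the number and percentage of subjects with a complication on the list closed before A4091058 unblinding. Beside it, report the number and percentage including later-identified events. Label both.
2. **SAP 6.1:** state that any later addition is made on treatment-masked listings by a role still blinded to parent treatment, and is applied by event type across all arms.

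Optional clarifications: name the endpoints covered by the first rationale bullet in Appendix 2; define the final phase 3 study in the heading of section 4.2; align both with protocol sections 5 and 9.2; and say whether the case report form reviews for rehabilitation, corrective procedures and analgesic use are done on masked listings.

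The cost is a few sentences, one extra column or table, and the preparation of masked listings. No complication is dropped, because both counts are shown, and no new data are needed.
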